- Clinical Safety: Only if the previous analysis had been done more than 1 month before the date of the Early Discontinuation visit.
- Echocardiogram: Only if the previous echocardiogram had been done more than 6 months before the date of the Early Discontinuation Visit.

PFIZER CONFIDENTIAL

CT02-GSOP Clinical Protocol Template Phase 1 2 3 4 (04 September 2018)

Fordadistrogene movaparvovec

C3391003

Final Protocol Amendment 15, 28 December 2023

Period	Year 2																				Long-term follow up	Early Discontinuation Visit
	Visit 20 ^{a,bb,cc}	Visit 21 ^{bb,cc}	Visit 22 ^{bb,cc}	Visit 23 ^{bb,cc}	Visit 24 ^{bb,cc}	Visit 25 ^{bb,cc}	Visit 26 ^{bb,cc}	Visit 27 ^{bb,cc}	Visit 28 ^{bb,cc}	Visit 29 ^{bb,cc}	Visit 29.2 ^{b,bb,cc}	Visit 30 ^{bb,cc}	Visit 30.1 ^{bb,cc}	Visit 30.2 ^{b,cc}	Visit 31 ^{c,cc}	Visit 31.2 ^{b,cc}	Visit 32 ^{b,cc}	Visit 33	Visit 34	Visit 35		
Visit Number/Description	Year 2, Week 1, Day 1	Year 2, Week 1, Day 2	Year 2, Week 1, Day 4	Year 2, Week 1, Day 6	Year 2, Week 1, Day 7	Year 2, Week 2, Days 8 & 9	Year 2, Week 2, Day 10	Year 2, Week 2, Day 14	Year 2, Week 3	Year 2, Week 4	Year 2, Week 5	Year 2, Week 6	Year 2, Week 7	Year 2, Week 9	Year 2, Week 11	Year 2, Week 13	Year 2, Week 18	Year 2, Week 35	Year 2, Week 52	Years 3, 4, 5, 6 ^d	Years 3, 4, 5, 6 ^d	
Visit Day	390	391	393	395	396	397& 398	399	403	410	417	423	431	437	449	463	479	509	629	749	930, 1290, 1650, 2010 ^d	1110, 1470, 1830, 2190 ^d	
Visit Window (\pm days)	3 ^f	2 ^f	2 ^f	2 ^f	2 ^f	2 ^f	2 ^f	3 ^f	3 ^f	3 ^f	3 ^f	3 ^f	3 ^f	3 ^f	3 ^f	3 ^f	3 ^f	7 ^f	7 ^f	30 ^f	30 ^f	

- FVC: Only If the previous FVC had been assessed more than 2 months before the date of the Early Discontinuation Visit.
- Viral vector shedding: For any given matrix, if the sample(s) had still been collected at the participant's last study visit, it should also be collected at the Early Discontinuation Visit.

f. **Visit Windows for Visits 20 through Visit 43**

- The number of days between each visit for Visit 20 (Year 2, IP administration) through Visit 43 must be maintained irrespective of the actual visit day of Visit 20, eg, if the actual visit day at Visit 20 is 392 (instead of 390), then Visit 21 will take place on Day 393 (instead of Day 391), etc.

g. **Brief physical and neurological examinations**, as described in [Section 8.2](#), are acceptable unless safety concerns warrant full examination.

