Visit Day	390	391	393	395	396	397& 398	399	403	410	417	423	431	437	449	463	479	509	629	749	930, 1290, 1650, 2010 ^d	1110, 1470, 1830, 2190 ^d	
Visit Window (\pm days)	3 ^f	2 ^f	2 ^f	2 ^f	2 ^f	2 ^f	2 ^f	3 ^f	3 ^f	3 ^f	3 ^f	3 ^f	3 ^f	3 ^f	3 ^f	3 ^f	7 ^f	7 ^f	7 ^f	30 ^f	30 ^f	

- n. The NSAA and CGIS will be administered by a single clinical evaluator at each visit and whenever possible, the same CE should administer the functional assessments (NSAA, ankle range of motion and FVC) for the same participant throughout the study. The NSAA, range of motion and FVC may be video recorded at the annual visits. If CE re-training is required, the assigned master physiotherapist may request additional visits to be recorded and reviewed. Whenever possible, motor functional assessments should be performed early in the course of the visit, to help reduce the effect of fatigue on the participants' performance; for additional advice regarding the ordering of assessments please consult the Functional Assessment Manual. On the following visits: Day 449 (Visit 31), Day 509 (Visit 33), Day 629 (Visit 34) and Day 749 (Visit 35), in which functional assessments (eg, NSAA) are performed, blood draws should always be done first, whenever possible, to ensure that the CK levels are obtained prior to the functional test; for additional advice regarding the ordering of assessments please consult the Functional Assessment Manual.
- o. An activity monitor may be placed on the participant's ankle prior to the performing of other functional assessments and is to be worn continuously for the subsequent 2 weeks.
- p. COAs will be completed by the caregiver on behalf of the participant and/or the participants themselves, depending on the participant's age and at the discretion of the Investigator and caregiver, as described in [Section 8.1.7](#).

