5.2. Exclusion Criteria

Participants are excluded from the study if any of the following criteria apply:

1. Prior treatment with gene therapy, defined as any therapy introducing exogenous DNA or intended to permanently alter the endogenous DNA. Gene therapy (other than IP) will be prohibited for the duration of the study.
2. Exposure within 6 months prior to Screening (Visit 1) to any treatment designed to increase dystrophin expression (including, but not limited to exon-skipping and nonsense read-through). These treatments will also be prohibited during the period

between Screening (Visit 1) and Day 1 (Visit 3) and for the first 52 weeks of the study. Please note that for participants who are eligible for these treatments:

Participants may be enrolled who have previously experienced lack of efficacy, or intolerance, as long as they received their last dose more than 6 months before screening (Visit 1), or who have refused these treatments.

Participants receiving these treatments from which there is believed to be benefit should not discontinue them in order to meet this exclusion criterion and enroll in the study.

3. Previous administration with an investigational drug or investigational vaccine within 30 days (or as determined by the local requirement) or 5 half-lives (whichever is longer) at Screening (Visit 1). These treatments will also be prohibited during the period between Screening (Visit 1) and Day 1 (Visit 3) and for the first 2 years of the study.
4. Known cognitive impairment or behavioral issues that would impede the ability to follow instructions, in the judgment of the Investigator, at Screening (Visit 1).
5. Any nonhealed injury at Screening (Visit 1) which, in the opinion of the Investigator, may impact functional testing; additionally, lower limb fractures must have been healed for at least 3 months prior to Screening (Visit 1).
6. Positive test for NAb to AAV9, based on the threshold determined by the Central Laboratory, from a sample taken at Screening (Visit 1).
7. Receipt of a live attenuated vaccination within 30 days prior to Screening (Visit 1). Receipt of a live attenuated vaccination will also be prohibited for 90 days before Day 1 (Visit 3), for 90 days prior to Year 2 IP administration, and for the first 2 months after each IP administration.
8. Abnormality in hematology or chemistry profiles at Screening (Visit 1). A single repeat for value(s) outside allowable limits is permitted to re-assess eligibility:

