Participants will also receive anesthesia according to the site standard of care for the muscle biopsies obtained in this study.

Vaccines

Participants will be able to receive any required live attenuated vaccine(s) only during the following periods:

1. Up to 90 days before Day 1 (Visit 3).
2. Day 60 (Visit 14) to Day 300. In addition, participants in Cohort 1 confirmed to meet exclusion criterion 15 will be allowed to receive any required live attenuated vaccine(s) for the remainder of the study. For details on the retrospective assessment of exclusion criterion 15, please see [Appendix 12](#).
3. Day 450 until the end of the study.

Participants will be able to receive an inactivated vaccine (eg, influenza, meningococcal, pneumococcal, *Haemophilus influenzae*) only during the following periods:

1. Up to 30 days before Day 1 (Visit 3)
2. Day 60 to Day 360 (Visit 19). In addition, participants in Cohort 1 confirmed to meet exclusion criterion 15 will be allowed to receive any required inactivated vaccine(s) for the remainder of the study. For details on the retrospective assessment of exclusion criterion 15, please see [Appendix 12](#).
3. Day 450 until the end of the study.

Participants will be able to receive an mRNA, or DNA-based, or non-replicating viral vector vaccine (eg, against SARS-CoV2) only during the following periods:

1. Up to 30 days before Day 1 (Visit 3)

2. Day 60 to Day 360 (Visit 19). In addition, participants in Cohort 1 confirmed to meet exclusion criterion 15 will be allowed to receive any required mRNA, or DNA-based, or non-replicating viral vector vaccine(s) (eg, against SARS-CoV2) for the remainder of the study. For details on the retrospective assessment of exclusion criterion 15, please see [Appendix 12](#).
3. Day 450 until the end of the study.

Other medications

With the exception of any prohibited therapies, other medications may be used if deemed necessary by the Investigator.

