Cohort 1 participants, as confirmed by the unblinded medical monitor, will not receive Year 2 IP administration, placebo, if they meet exclusion criterion 15. They will not require post-IP safety monitoring in Year 2, will not attend Visit 18 in Year 1 and Visits 20 to 30.2 in Year 2, and will not receive their protocol-mandated glucocorticoid regimen in Year 2. These participants will remain in the study for safety monitoring as described in [Appendix 12](#).

Once the unblinded medical monitor has communicated to the Investigator that the participant meets eligibility criteria based on laboratory tests and echocardiographic results, then the Investigator will ensure that none of the criteria listed below are met before allowing IP administration.

To preserve the blinding of the treatment assignment for the site and for the Sponsor, the following criteria will be assessed for both Cohort 1 and Cohort 2 participants.

7. Receipt of a live attenuated vaccination within 90 days prior to Day 390 (Visit 20). If a participant has received a live attenuated vaccination within 90 days prior to Day 390 (Visit 20), IP administration must be delayed until at least 90 days after the last administration of the vaccine.
8. Receipt of an inactivated vaccine (eg, influenza, meningococcal, pneumococcal, *Haemophilus influenzae* vaccination) within 30 days prior to Day 390 (Visit 20). If a participant has received an inactivated vaccine within 30 days prior to Day 390 (Visit 20), IP administration must be delayed until at least 30 days after the last administration of the vaccine.
9. Receipt of an mRNA or DNA-based, or non-replicating viral vector vaccine (eg, against SARS-CoV2) within 30 days of Day 390 (Visit 20). If a participant has received any of the above-listed vaccines within 30 days prior to Day 390 (Visit 20), IP administration must be delayed until at least 30 days after the last administration of the vaccine.
10. Receipt of any systemic immunosuppressant agents other than glucocorticoids, and/or systemic antiviral therapy, and/or interferon. If a participant has received any of these therapies, IP administration must be delayed until at least 30 days after the last dose.
11. Acute infection at Day 360 (Visit 19) that, in the judgement of the Investigator, is not expected to be fully resolved at least 14 days prior to IP administration on Day 390 (Visit 20).

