12. Additionally, any participant, in Cohort 1 or Cohort 2, who has received gene therapy (other than IP) after Year 1 IP administration will not be eligible for Year 2 IP administration but will not be withdrawn from the study.

If any of the above eligibility criteria (7-11) are met for Cohort 1 or Cohort 2 participants, IP administration will be delayed until none of the criteria are met. If the time between the blood draw for the clinical safety laboratory tests on Day 360 Visit (Visit 19) and the planned Day 390 Visit (Visit 20) exceeds 13 weeks (90 days), due to operational or administrative reasons (eg, enrollment pause due to regulatory or safety review, operational issues causing significant delays), then the clinical safety laboratory tests should be repeated and eligibility (re)confirmed prior to administering IP. The participant will not be withdrawn due to exceeding the time between Day 360 Visit (Visit 19) and Day 390 Visit (Visit 20).

If a Cohort 2 participant is determined to be *permanently* ineligible for Year 2 IP administration, because of a confirmed result for the hematology or chemistry profiles outside allowable limits or because of a positive test for NAb to AAV9, based on the threshold determined by the Central Laboratory, he will be withdrawn from the study. The medical monitor will inform the site of the decision, to allow the site to communicate with the participant and the caregiver. In this circumstance, no Early Discontinuation Visit will be required.

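### Section 6.5.1 reopens live vaccines on a fixed Day 450, which fits exclusion 7's 2-month ban after each IP dose only if Year 2 IP is given at about Day 390

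*Protocol*

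**What the plan says.** **The ban.** Section 5.2, exclusion 7, prohibits live attenuated vaccines "for 90 days prior to Year 2 IP administration, and for the first 2 months after each IP administration". Both limits are counted from the dose.

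**The permitted periods.** Section 6.5.1 (Vaccines) says live attenuated vaccines may be given only in listed periods. After Year 1 IP the period is "Day 60 (Visit 14) to Day 300", whose start is tied to a visit. After Year 2 IP it is "Day 450 until the end of the study", with no visit, no dose date and no reference to exclusion 7. Section 6.5.2 (Prohibited Therapies) does not mention vaccines.

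**Delay of the Year 2 dose.** Section 7.1, criterion 10, covers systemic immunosuppressants other than glucocorticoids, antivirals and interferon: "If a participant has received any of these therapies, IP administration must be delayed until at least 30 days after the last dose". Criterion 11 covers acute infection. For criteria 7 to 11 the general rule is that "IP administration will be delayed until none of the criteria are met", and no maximum is given.

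**Day counting.** Footnote f to the Year 2 Schedule of Activities (Section 1.3.2) says that the spacing of visits from Visit 20 onward "must be maintained irrespective of the actual visit day of Visit 20". Its example is: "if the actual visit day at Visit 20 is 392 (instead of 390), then Visit 21 will take place on Day 393". Section 5.3.2 restarts the day count at the Year 2 dose, but within the text on operational or administrative pauses.

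**The concern.** A limit counted from the dose and a limit fixed in study days give the same date only when the dose falls on its nominal day. If Year 2 IP is given late, Day 450 does not move and the ban in exclusion 7 does. The permitted-therapies section then allows what the exclusion criterion forbids.

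A site deciding whether a boy may have a live vaccine would naturally look in the vaccine paragraph of Section 6.5.1. For a boy dosed late, the date there is too early. He may be a Cohort 2 boy who has just received the vector, and he would still be on the protocol-mandated glucocorticoid course, which runs for 90 days after IP. The pre-dose checks in Section 7.1 cannot catch the error, because the dose has already been given.

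**Working it through.** **Inputs**
- Nominal Year 2 dose: Day 390 (Visit 20), window ±3 days (Section 1.3.2).
- Ban after the dose: 2 months (exclusion 7). No day count is given, so I take 59, 60 and 61 days. The Year 1 list implies 59, from Day 1 to Day 60.
- Live vaccines reopen on Day 450 (Section 6.5.1).
- Washout after an antiviral: at least 30 days from the last dose (Section 7.1, criterion 10).
- Antivirals are allowed for an acute viral infection (Section 6.5.2), so such a delay involves no deviation.

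**Reproducing the plan's dates**
- 390 + 60 = 450, the stated Day 450.
- 390 − 90 = 300, the stated end of the Year 1 period.
- Both dates therefore come from a dose on Day 390.

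**Latest Year 2 dose for which Day 450 respects the ban** (450 − m, where m is the length of 2 months in days)
- m = 59: Day 391.
- m = 60: Day 390.
- m = 61: Day 389.

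**Shortfall for a later dose**

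Days after IP on Day 450 = 450 − dose day. Shortfall = m − (450 − dose day).

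| Situation | Dose day | Days after IP on Day 450 | Shortfall, m = 59 / 60 / 61 |
|---|---|---|---|
| Upper limit of Visit 20 window | 393 | 57 | 2 / 3 / 4 |
| Infection resolved on Day 390, then 14 days clear | 404 | 46 | 13 / 14 / 15 |
| Last antiviral dose on Day 380 (380 + 30) | 410 | 40 | 19 / 20 / 21 |
| Last antiviral dose on Day 389 (389 + 30) | 419 | 31 | 28 / 29 / 30 |

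In the last row the correct reopening date is 419 + 60 = Day 479 (Day 478 on the 59-day count). Under footnote f, Visit 31, nominally Day 449 and so 59 days after the dose, moves to 419 + 59 = Day 478. The vaccine date names no visit and stays at Day 450. At 31 days after IP the boy is on the first day of the 1.0 mg/kg/day glucocorticoid step (days 31 to 60 in Section 6.5.1).

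With Visit 19 on Day 360, a dose on Day 419 is 59 days later. That exceeds the 55-day limit for the neutralizing-antibody sample in Section 7.1, so a Cohort 2 boy would need a second negative test. The test is permitted, so this does not cap the delay.

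**The case against.** **Exclusion 7 already governs.** It is worded as a rule for the conduct of the study, counts from each dose and covers Year 2. A site that applies both rules waits the full 2 months. This stands, and it is the main reason the point is minor. It does not remove the inconsistency: Section 6.5.1 states the permitted periods without qualification or cross-reference.

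**Day 450 may be a nominal label.** The protocol often uses Day 390 (Visit 20) to mean the dosing day, whenever it falls. Examples are the instruction in Section 6.5.1 not to take background steroid that day, Section 7.1 criteria 7 to 9, and the Cohort 2 safety set in Section 9.3. On that usage Day 450 means 60 days after the dose and nothing conflicts. The reading is possible. Against it, footnote f moves visits to later day numbers and does not renumber the days, the only stated recount is in the pause text of Section 5.3.2, and Day 450 carries no visit label that could move with the dose. Neighbouring rules that are meant to follow the dose say so, such as the steroid steps in Section 6.5.1 and the interferon limit in Section 6.5.2.

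**The in-window difference is trivial.** A shortfall of 2 to 4 days cannot be resolved against a limit written as 2 months. I accept this and make nothing of it.

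**The group is small.** It takes an out-of-window delay that is not a pause, a required live vaccine within a few weeks of Day 450, and a site that overlooks exclusion 7. Only Cohort 2, about 33 of 99 participants, receives vector in Year 2. This also stands.

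**Conclusion.** The point holds as a minor safety inconsistency. Day 450 agrees with exclusion 7 only for a Year 2 dose at about Day 390. After a later dose outside a pause, with day numbers running on as in footnote f, Section 6.5.1 permits a live vaccine within the banned 2 months. In the worked example Day 450 is 31 days after IP, 28 to 30 days short. Confidence is medium, because the nominal-day reading cannot be excluded.

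Stronger conclusions that a reader might draw are not supported:
- **About 4 weeks as a maximum.** It is one scenario. Section 7.1 states no maximum delay, and an antiviral course ending later would move the dose further.
- **A shortfall of nearly 3 months.** A live vaccine on Day 389 would delay IP to Day 479 under criterion 7, after Day 450 has passed. That requires a live vaccine after the permitted Day 300, so a deviation has already occurred.
- **The same conflict for inactivated or mRNA vaccines, or after pauses.** Exclusion 7 covers live attenuated vaccines only, and Section 5.3.2 has its own day-count rule for pauses.
- **An effect on the trial's result.** The Week 52 visit (Day 360) precedes all of this, so the primary endpoint, power and alpha are unaffected.

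**What to change.** In the live-vaccine list of Section 6.5.1, replace Day 450 with 2 months (60 days) after the actual Year 2 IP administration. State that participants who will not receive Year 2 IP keep Day 450 or have no restriction. Cohort 1 participants confirmed to meet exclusion criterion 15 are already exempt in that list.

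The cost is one line of wording. The interval is already in exclusion 7, and a boy dosed on Day 390 keeps Day 450. The same wording could be used in the other two vaccine lists for uniformity, though nothing in this point requires it.

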6.5.2. Prohibited Therapies

The following therapies are prohibited from the time of signing the informed consent until the end of Year 2. After Day 749 (Visit 35) participants will be able to receive any of the therapies listed below, if deemed necessary. For Cohort 1 participants confirmed to meet exclusion criterion 15 and for participants who declined Year 2 IP administration (see [Section 7.2.1](#)), the medications listed below will be prohibited only until the end of Year 1. After Day 360 (Visit 19) these participants will be able to receive any of the therapies listed below, if deemed necessary. For details on the retrospective assessment of exclusion criterion 15, please see [Appendix 12](#).

1. **Immunosuppressant agents** (other than glucocorticoids, see [Section 6.5.1](#)) unless administered in response to immunologic reaction.
2. **Investigational therapies**, including those being evaluated for the treatment of DMD (eg, idebenone, tamoxifen).
3. **Antiviral therapy**, unless administered to treat an acute viral infection (eg, COVID-19).
4. **Interferon therapy**, unless administered to treat an acute viral infection and the participant is at least 2 months post IP administration.

Any therapy designed to increase dystrophin expression (including, but not limited to exon skipping and nonsense read-through) will be prohibited during the first 52 weeks of the study. When participants have completed Day 360 (Visit 19), if the Investigator determines that, due to worsening of DMD, an approved therapy with this mechanism were deemed necessary, such therapy would then be allowed.

Gene therapy, defined as any therapy introducing exogenous DNA or intended to permanently alter the endogenous DNA, will be prohibited from the signing of the informed consent until the end of the study.

6.5.3. Rescue Medicine

Not applicable.

6.6. Dose Modification

Not applicable.

6.7. Intervention After the End of the Study

No intervention will be provided to study participants at the end of the study.

7. DISCONTINUATION OF STUDY INTERVENTION AND PARTICIPANT DISCONTINUATION/WITHDRAWAL

7.1. Discontinuation of Study Intervention

In the context of this study, treatment will consist of two single intravenous infusions, one of fordadistrogene movaparvovec and one of placebo (Section 4.1). Following IP administration on Day 1 (Visit 3), the only potential for discontinuation of study intervention is at the time of IP administration in Year 2. Cohort 1 participants will receive placebo on Day 390 (Visit 20) and will not be discontinued from study intervention although the timing of IP administration may be affected by eligibility criteria, as described below, in order to preserve the blinding of the ongoing study. Cohort 2 participants are scheduled to receive fordadistrogene movaparvovec one year after receiving placebo if they remain eligible for Year 2 IP administration. Participants in Cohort 2 who are determined to be ineligible to receive fordadistrogene movaparvovec by the criteria listed below (1-6) will discontinue study intervention.

Cohort 2 participants will be confirmed to be eligible for Year 2 IP administration before receiving treatment with fordadistrogene movaparvovec. There are no eligibility criteria for Cohort 1 participants for Year 2 IP administration based on the results of hematology and chemistry profiles or of results of testing for NAb to AAV9, but they will be reviewed for safety reasons. In order to preserve the blinding of the ongoing study, an unblinded, medically qualified monitor (medical monitor), independent from the team conducting and monitoring the study, will be the only person to review the results of the hematology and chemistry profiles as well as of the NAb to AAV9. These laboratory results will be blinded to the site and the Sponsor.

Additionally, the unblinded medical monitor will determine if any test(s) should be repeated (due to a result outside of allowable limits for Year 2 IP administration eligibility considered possibly transient for Cohort 2 participants, and/or due to test showing a potential safety issue considered possibly transient for Cohort 1 and Cohort 2 participants). The unblinded medical monitor will also decide if any result(s) must be unblinded to the site and the Sponsor, in the unlikely event that it reflects a safety issue.

Cohort 2 participants will not be eligible for Year 2 IP administration if they present with any of the following:

1. Positive test for NAb to AAV9, based on the threshold determined by the Central Laboratory, at Day 360 (Visit 19). If the time between Day 360 (Visit 19) and Day 390 (Visit 20) is more than 55 days, a second NAb to AAV9 test must be performed and confirmed to be negative before Year 2 IP administration. Dosing cannot occur unless there is a negative NAb to AAV9 test from a sample collected 55 or less days before the day of IP administration, as reviewed by the unblinded medical monitor.
2. Abnormality in hematology or chemistry profiles at Day 360 (Visit 19). A single repeat for value(s) outside allowable limits is permitted to re-assess eligibility:
 - Absolute neutrophil count <1000 cells/mm³;
 - Platelets <150 x 10³/μl;
 - Cystatin C >1.2 x ULN;

Positive hepatitis A virus (anti-HAV) immunoglobulin M, hepatitis B surface antigen (HbsAg), and/or hepatitis C antibody (HCVAb);

Markers of hepatic inflammation or overt or occult cirrhosis as evidenced by one or more of the following:

 - PT > ULN; prolonged INR >ULN;
 - GLDH >2 x ULN;
 - Total bilirubin >1.5 x ULN (unless the participant has a history of Gilbert disease) and direct bilirubin >0.5 mg/dL;
 - GGT >1.5 x ULN.

Additionally, the unblinded medical monitor will confirm the treatment allocation for participants with the conditions listed below, so those participants in Cohort 2 who meet any of these conditions do not receive Year 2 IP administration and are withdrawn from the study:

3. Participants screened or randomized who had not yet received Year 2 IP administration and were retrospectively confirmed to meet exclusion criterion 15 (see [Appendix 12](#)).
4. LVEF <50% on echocardiogram performed at Day 360 (Visit 19), or at the unplanned visit to re-assess eligibility for Year 2 IP administration.

5. Diagnosis of current or prior myocarditis by a pediatric cardiologist.
6. Not a candidate for mechanical cardiac or respiratory support, or any other invasive intervention, if indicated for management of an acute event as determined by the cardiologist in consultation with the investigator.

Cohort 1 participants, as confirmed by the unblinded medical monitor, will not receive Year 2 IP administration, placebo, if they meet exclusion criterion 15. They will not require post-IP safety monitoring in Year 2, will not attend Visit 18 in Year 1 and Visits 20 to 30.2 in Year 2, and will not receive their protocol-mandated glucocorticoid regimen in Year 2. These participants will remain in the study for safety monitoring as described in [Appendix 12](#).

Once the unblinded medical monitor has communicated to the Investigator that the participant meets eligibility criteria based on laboratory tests and echocardiographic results, then the Investigator will ensure that none of the criteria listed below are met before allowing IP administration.

To preserve the blinding of the treatment assignment for the site and for the Sponsor, the following criteria will be assessed for both Cohort 1 and Cohort 2 participants.

7. Receipt of a live attenuated vaccination within 90 days prior to Day 390 (Visit 20). If a participant has received a live attenuated vaccination within 90 days prior to Day 390 (Visit 20), IP administration must be delayed until at least 90 days after the last administration of the vaccine.
8. Receipt of an inactivated vaccine (eg, influenza, meningococcal, pneumococcal, *Haemophilus influenzae* vaccination) within 30 days prior to Day 390 (Visit 20). If a participant has received an inactivated vaccine within 30 days prior to Day 390 (Visit 20), IP administration must be delayed until at least 30 days after the last administration of the vaccine.
9. Receipt of an mRNA or DNA-based, or non-replicating viral vector vaccine (eg, against SARS-CoV2) within 30 days of Day 390 (Visit 20). If a participant has received any of the above-listed vaccines within 30 days prior to Day 390 (Visit 20), IP administration must be delayed until at least 30 days after the last administration of the vaccine.
10. Receipt of any systemic immunosuppressant agents other than glucocorticoids, and/or systemic antiviral therapy, and/or interferon. If a participant has received any of these therapies, IP administration must be delayed until at least 30 days after the last dose.
11. Acute infection at Day 360 (Visit 19) that, in the judgement of the Investigator, is not expected to be fully resolved at least 14 days prior to IP administration on Day 390 (Visit 20).

12. Additionally, any participant, in Cohort 1 or Cohort 2, who has received gene therapy (other than IP) after Year 1 IP administration will not be eligible for Year 2 IP administration but will not be withdrawn from the study.

If any of the above eligibility criteria (7-11) are met for Cohort 1 or Cohort 2 participants, IP administration will be delayed until none of the criteria are met. If the time between the blood draw for the clinical safety laboratory tests on Day 360 Visit (Visit 19) and the planned Day 390 Visit (Visit 20) exceeds 13 weeks (90 days), due to operational or administrative reasons (eg, enrollment pause due to regulatory or safety review, operational issues causing significant delays), then the clinical safety laboratory tests should be repeated and eligibility (re)confirmed prior to administering IP. The participant will not be withdrawn due to exceeding the time between Day 360 Visit (Visit 19) and Day 390 Visit (Visit 20).

If a Cohort 2 participant is determined to be *permanently* ineligible for Year 2 IP administration, because of a confirmed result for the hematology or chemistry profiles outside allowable limits or because of a positive test for NAb to AAV9, based on the threshold determined by the Central Laboratory, he will be withdrawn from the study. The medical monitor will inform the site of the decision, to allow the site to communicate with the participant and the caregiver. In this circumstance, no Early Discontinuation Visit will be required.

